Remuneration. Participants will be remunerated a total of \$275 via the ClinCard system, according to the following payment schedule, upon completion of all study visit procedures.

Study Visit	Compensation
Screening Visit (Visit 1)	\$40
Enrollment Visit (Visit 2)	\$40
Month 1 Visit (Visit 3)	\$65
Month 2 Visit (Visit 4)	\$65
Month 3 Visit (Visit 5)	\$65
Total	\$275

TruTag System. The TruTag system leverages a silica-based FDA generally regarded as safe (GRAS) microparticle that is incorporated into the coating of B/F/TAF. When light shines from a smartphone camera onto the coated drug, the reflected optical image is interpreted as B/F/TAF. A corresponding app records each scan as an adherence event and patients using the TruTag system are coached to scan their medication prior to ingesting it. Dissolution of B/F/TAF when overcoated with the TruTag system was tested by Gilead Sciences, demonstrating that there is no change in dissolution. Specialty coated B/F/TAF will be provided through a cooperative agreement between Gilead Sciences and TruTag. In brief, B/F/TAF from the Gilead manufacturing supply chain will be overcoated with the TruTag system by ThermoFisher, the Gilead contract coating manufacturer. Drug will then be shipped in bottles of 30 to the Fenway Health Pharmacy.

In addition to recording adherence events, the TruTag app also provides a calendar for participants to review their adherence on-demand, as well as reminder systems that are triggered if no adherence event is detected by the TruTag system during a 24-hour period. Finally, the app

provides a secure platform to facilitate two-way text message communication between participants and the study team. This platform will be used to provide study-related reminders and communication in the setting of detected nonadherence.

In-Study Messaging. Participants will receive communications via the TruTag app during their participation in the study. Messaging will include: (1) daily adherence reminders, (2) reminders following detected nonadherence, (3) study-related reminders of upcoming visits, and (4) responses to technology-related questions.

Daily Adherence Reminders. During installation of the TruTag app, study staff will ask participants what time of day they expect to take their daily B/F/TAF dose. We will set up daily adherence reminders in the app for 10 minutes prior to their expected dosing period.

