Detected Nonadherence Reminders. The TruTag app will also be programmed to provide adherence reminders 60 minutes after the end of a dosing period, in the event that no ingestion has been detected. Additionally, if 48 hours of nonadherence is detected (i.e., 2 days of missed ingestions), study staff will utilize the two-way texting in the app to check in with participants. If participants do not respond to these nonadherence reminders, the study team will call or message participants to ensure that recorded nonadherence is not related to technological issues (i.e., related to operation of the TruTag system).

Study-Related Reminders. The TruTag app will be programmed to send reminders to participants in advance of each upcoming study visit. Reminders will be sent at 48 and 24 hours prior to the scheduled visit date.

Technology-Related Questions. We will encourage participants to report any technologyrelated questions and/or challenges to the study team via the TruTag app. We anticipate that these may include questions about how to operate the TruTag app, scan medication, or possible updates or reinstallations of the app. We will attempt to address technology-related issues through in-app messaging. If unsuccessful, we will contact participants by phone to troubleshoot technological concerns. if further assistance is required, we will schedule a study visit to assist participants with technology-related issues.

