Data Collection. Quantitative data will be collected via the baseline quantitative assessment at the Enrollment Visit (Visit 2), and via the System Usability Scale at the Month 3 Visit (Visit 5). Study staff will collect participant monthly adherence via the TruTag application and create timeline followback discussions at the Month 1 Visit (Visit 3), Month 2 Visit (Visit 4), and Month 3 Visit (Visit 5) to identify and contextualize adherence events of interest across the study period. Qualitative data will be collected via individual qualitative interviews at the Month 3 Visit (Visit 5). Dried blood spot testing will be conducted at the Screening Visit (Visit 1) and the Month 3 Visit (Visit 5). Lastly, general participant TruTag application usage will be collected to better understand participant engagement with the application. This will include: app engagement, including time spent in the app and which screens of the application participants access along with the frequency and time in which they spend on each screen on the application, as well as reminder data, including number of reminders delivered, timing of reminders, dosing window around which reminders will be sent, and conversion rate (days in which a reminder is delivered and adherence event recorded afterwards in the TruTag appl.

Baseline Quantitative Assessment. Quantitative data, including questions related to sociodemographics, use of ART, sexual history, mental health, attitudes about technology, medical mistrust, and substance use will be collected via a quantitative assessment. Quantitative data will be stored and managed on the REDCap platform hosted at TFI.

System Usability Scale. Participants will complete the System Usability Scale (SUS)¹¹ at the Month 3 Visit (Visit 5). The SUS is a 10-item Likert scale which will assess participants' perceptions of the usability of TruTag technology.

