Qualitative Interview. Qualitative data will be collected via individual, qualitative interviews. Interviews will follow a semi-structured guide, which contains key content areas, including overall perceptions of the TruTag technology, perspectives about this technology in the context of ART treatment, potential applications for the technology and associated adherence data, privacy and health-related concerns, and future recommendations. The interview guide will be semi-structured and will allow for interviews to be adapted based on participants' responses. Qualitative interviews will be conducted until thematic saturation is reached.

Study Outcomes. The primary outcomes will be the feasibility and acceptability of the TruTag system during the 90-day study period, which will be assessed through participant recruitment and engagement with the technology via adherence data, qualitative interviews at the end of the study, and quantitative assessments (i.e. SUS survey). We will additionally collect biological (HIV viral load) and pharmacologic (dried blood spot) data for a secondary outcome, which will be to correlate TruTag-recorded adherence with other traditional ART adherence measures.

Data Storage and Transfer. Secure Business Dropbox, hosted at Mass General Brigham (MGB), will be used for file storage in this study. Quantitative data will be stored and managed on the REDCap platform hosted at TFI. Quantitative assessments and qualitative interview transcripts will not be made publicly available. De-identified data may be shared with the study sponsor (TruTag). Audio files from qualitative interviews will be sent to Landmark Associates, Inc., a HIPAA-compliant external transcription company, via their online portal. Audio files will be removed from recording devices and from the Landmark portal when transcripts are available for download. Transcript files will be stored in access-protected folders behind the TFI firewall, accessible only to approved members of the study team. A secure Excel spreadsheet linking Study ID numbers to participants' names will be maintained in the same fashion.

7. Risks and Discomforts.

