Risks of Psychological Discomfort while Completing Assessments. Study questionnaires and interviews may include questions that individuals do not feel comfortable answering, or that may cause psychological discomfort. Individuals will be informed during the consent process that they may choose to skip any questions that they do not want to answer. They will also be reminded that they may withdraw from the study at any time, for any reason, without penalty.

Risks of Blood Draws. Participants will be informed during the consent process that they may have a bruise or pain from the site where blood samples are drawn. There is also a small risk of infection, lightheadedness, and/or fainting. To mitigate this risk, all study staff will be trained in phlebotomy at Fenway Health. We will ask participants who have a history of vasovagal syncope from blood draws to lie flat or sit in a recliner prior to blood draw. We will also have oral fluids available for participants at visits where blood draws are required.

8. Benefits.

Individuals may not benefit directly from participation in this study. They may indirectly benefit from learning about the TruTag system as a tool for measuring their ART adherence behaviors.

9. Statistical Analysis.

We will calculate basic descriptive statistics for key demographic variables. SUS scores will be summed and a mean score will be calculated for each participant. Overall SUS will be measured at each month during study participation. We will measure adherence via three strategies: (1) TruTag recorded adherence, (2) pill count at each monthly study visit, and (3) dried blood spot tenofovir alafenamide concentration. Correlation coefficients will be calculated between each of these adherence metrics. To measure if correlation of measures degrades over time (e.g., if individuals disengage from the TruTag system and stop using it over time), we will use a point biserial correlation.

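### TruTag and pill count are compared only by correlation, so no planned statistic gives the size or direction of their disagreement; add the paired difference and capture rate for each visit interval.

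*Combined protocol and SAP*

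**What the plan says.** Section 9 (Statistical Analysis) names three adherence measures: TruTag recordings, "2) pill count at each monthly study visit", and the dried blood spot (DBS) drug concentration. The planned comparison is one sentence: "Correlation coefficients will be calculated between each of these adherence metrics". The type of coefficient and the time unit are not given.

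For change over time, the stated worry is what happens "if individuals disengage from the TruTag system and stop using it over time". The tool is a point biserial correlation whose two variables are not named. The descriptive statistics promised in that section cover demographic variables only.

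Section 6 (Study Outcomes) words the secondary outcome the same way, "which will be to correlate TruTag-recorded adherence with other traditional ART adherence measures". No paired difference, limits of agreement or capture rate appears anywhere.

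The data for them are nevertheless collected. Section 6 (TruTag System) says "A corresponding app records each scan as an adherence event", and Section 6 (Data Collection) says "Study staff will collect participant monthly adherence via the TruTag application". Thirty pills are dispensed for each interval, and unused pills are returned and counted at the Month 1, 2 and 3 visits.

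**The concern.** DBS is a concentration, so correlation is a natural choice there. TruTag and pill count are different: both are counts of daily doses over the same days. What a reader needs to know is how many doses taken according to pill count were not scanned, and whether that shortfall grows.

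A correlation coefficient does not answer this. It is unchanged if everyone's scans fall short by a constant number or a constant proportion. When it does move, it mixes the capture rate with the spread of adherence and with person-to-person variation in scanning. A reader given only r cannot tell whether TruTag runs 5 or 19 points below pill count. A falling r is also only an indirect sign of the disengagement that Section 9 is worried about.

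**Working it through.** **Inputs from the documents.** N = 15; one pill a day; 3 intervals × 30 pills = 90 doses. The plan states no r, SD, capture rate or precision target, so there is no planned figure to reproduce. Everything below on adherence and capture is assumed.

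**Step 1: r can miss a shortfall completely.** Take 15 assumed monthly pill counts between 24 and 30 doses, totalling 427. Let TruTag record 0, 6 and 12 fewer doses per person in Months 1, 2 and 3.

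- r = 1.000 in every month.
- Mean difference: 0, -6 and -12 doses, that is 0, -20 and -40 points of 30.
- Capture rate: 427/427 = 100%, (427 - 90)/427 = 78.9%, (427 - 180)/427 = 57.8%.

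**Step 2: with random misses r moves, but does not identify capture.** Simulation of 20,000 trials of 15 people over 90 days: pills taken are binomial with beta-distributed adherence, and scans are binomial on pills taken with beta-distributed capture. Expected difference in points = adherence × (capture - 1); for example 95 × (0.80 - 1) = -19.0 and 95 × (0.95 - 1) = -4.75.

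| Adherence mean/SD (%) | Median r: 80% capture uniform v 95% capture, scan SD 5 | Difference (points) | Median r, scan SD 5 in both |
|---|---|---|---|
| 95/3 | 0.60 v 0.60 | -19.0 v -4.75 | 0.44 v 0.60 |
| 90/8 | 0.87 v 0.87 | -18.0 v -4.5 | 0.76 v 0.87 |
| 80/15 | 0.96 v 0.96 | -16.0 v -4.0 | 0.92 v 0.96 |

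The equal-r columns need unequal scan variation. With equal variation r ranks the two correctly on average, but in a single trial r at 80% capture is at least r at 95% in 29%, 20% and 16% of runs when both use the same pill counts (31%, 25% and 22% with independent samples). Over the three samples and scan SDs of 0 to 10 points, median r spans 0.29 to 0.96 at 80% capture and 0.43 to 0.99 at 95%. An observed r therefore does not point back to a capture rate.

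**Step 3: precision at n = 15.**

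- Half-width of the 95% CI for a mean paired difference = t(0.975, 14)/√15 × SD = 0.554 × SD of the differences.
- Over 90 days this is 2.3 to 5.6 points at 80% capture (scan SD 0 to 10) and 2.3 to 4.5 at 95% capture (scan SD 5 to 10).
- Coverage is 94-95% at 80% capture. At 95% capture it is 91-92% with scan SD 5 and about 83% with SD 10, because the losses are skewed.
- Limits of agreement lie about ±8 to ±20 points around the mean, each limit with a CI of about ±4 to ±10.
- For comparison, an observed r of 0.7 at n = 15 has a 95% CI of 0.29 to 0.89 (Fisher z).

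**Step 4: disengagement by month** (95/3 sample, scan SD 5, capture redrawn each month). Capture falling 95, 87.5, 80% and capture flat at 87.5% give the same 90-day difference (-11.9) and nearly the same 90-day r (0.62 v 0.61). By month the falling pattern gives -4.75, -11.9 and -19.0 points, against -11.9 each month. Month 3 minus Month 1 is -19.0 - (-4.75) = -14.25, with half-width 5.6 (8.1 at scan SD 10); its CI excludes 0 in 99.6% (88%) of runs. Median monthly r falls from 0.65 to 0.43 at scan SD 5, yet Month 3 r is at least Month 1 r in 24% (31%) of runs.

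**Step 5: pill-count error.** If half of unused pills are not returned and are counted as taken, the difference shifts by (100 - 95)/2 = 2.5, (100 - 90)/2 = 5 and (100 - 80)/2 = 10 points. True 80% capture then reads 76/97.5 = 78%, 72/95 = 76% and 64/90 = 71%. True 95% capture reads 93%, 90% and 84%. In the 80/15 sample, 95% capture with poor return gives 76 - 90 = -14.0, close to 80% capture with full return at 64 - 80 = -16.0. The shift cancels in Month 3 minus Month 1 if return is equally poor each month. If only Months 1 and 2 are affected, that change shrinks from -14.25, -13.5 and -12.0 to -11.75, -8.5 and -2.0.

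**The case against.** **The stakes are small.** This is one pairing in a secondary outcome whose stated aim is to correlate. No go/no-go rule depends on r, and the difference could be computed later from the same data. All of that stands, and it limits the weight of the point.

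**Other elements cover disengagement.** Section 6 collects app use, reminder conversion and timeline followback. It also provides that "Additionally, if 48 hours of nonadherence is detected (i.e., 2 days of missed ingestions), study staff will utilize the two-way texting" to check in, with further contact "to ensure that recorded nonadherence is not related to technological issues". These help explain missed scans, but none is a planned statistic against pill count. The trigger itself cannot separate missed doses from missed scans. At 80% capture with 95% adherence, or 95% capture with 80% adherence, 76% of days are recorded. With independent daily misses of probability 0.24, both give 0.24² + 88 × 0.76 × 0.24² = 3.9 runs of two or more missed days per person in 90 days. The participants' answers may separate the two cases, but no analysis of those answers against pill count is planned.

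**The point biserial could be run on the discrepancy by early and late period.** That would show the direction of change. The plan does not say so, and the result would be unit-free, with no level of disagreement and no monthly value.

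**Pill count is no gold standard.** This stands and is the main limit. With half of unused pills unreturned (80% capture, scan SD 5), the CI covers the true scan shortfall in only about 73%, 23% and 0.1% of runs across the three samples, while median r moves little (0.44 to 0.37, 0.76 to 0.71, 0.92 to 0.88). The simulation also excludes scans without ingestion, so its negative direction is assumed. The difference must be reported as agreement with pill count only.

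**Conclusion.** The concern holds. Every planned comparison of TruTag with pill count is a correlation, so the plan gives neither the size nor the direction of disagreement, overall or by month. Under the assumed inputs, captures whose differences from pill count are about 12 to 14 points apart (-16.0 v -4.0 to -19.0 v -4.75) can share the same median r when scanning is uniform at the lower capture and varies at the higher. With equal variation r ranks them correctly on average but still gives no capture rate. The paired difference separates such cases at n = 15 if pill return is good, and less well if it is not. All adherence, capture and variation figures are assumptions. The change is worth making because it is cheap and speaks directly to the disengagement question in Section 9. It does not threaten the primary feasibility and acceptability outcomes.

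**What to change.** In Section 9, for TruTag against pill count, report for each between-visit interval (Months 1, 2, 3) and overall:

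- the mean paired difference, TruTag % minus pill-count %, over the same days with one scan-day per calendar day, with 95% CI. State the percentage denominator, since visits are only approximately 30 days apart, and note that the t interval can undercover when capture is high and losses are skewed;
- the capture rate, scan-days divided by pills dispensed minus pills returned;
- Bland-Altman limits of agreement, labelled imprecise at n = 15.

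Make Month 3 minus Month 1 of the paired difference, with 95% CI, the measure of disengagement from scanning. Flag intervals whose visit was held remotely (allowed at Months 1 and 2), because pill return may differ there. Keep the correlations, with 95% CIs, as supportive. For DBS keep correlation and use the Month 3 sample, since the screening sample predates TruTag use. State that the difference measures agreement with pill count, not error against true ingestion.

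The cost is a few SAP lines and no new data. The drawback is that the difference and the capture rate both inherit pill-count error, and precision is modest.

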Prior qualitative work among persons living with HIV (PLWH) has demonstrated that the TruTag system is acceptable as a strategy to measure ART adherence. Participants also reported interest in leveraging the app to receive information around HIV, sexual health and their clinical care including appointment times and testing reminders. Importantly, participants described the system as easy to operate and did not report privacy concerns. As an extension of this qualitative work, this proposal seeks to conduct an open label, pilot demonstration trial that tests the feasibility and acceptability of operating the TruTag system to measure ART adherence in real-world settings.

2. Specific Aims and Objectives.

The aim of this study is to conduct an open-label pilot demonstration trial to understand the feasibility and acceptability of the TruTag system to measure ART adherence with N=15 individuals living with HIV who are currently on ART.

3. General Description of Study Design.

This is an open-label pilot demonstration trial. We will enroll N=15 individuals living with HIV who are taking Bictegravir/emtricitabine/tenofovir alafemate (Biktarvy) as ART, who will utilize the TruTag system to measure ART adherence over a 90-day period.

The participant will use the TruTag coated ART for 90 days with the TruTag application on their smartphone. In this study, participants will scan their coated ART medication before swallowing their medication, and this scanning event will link to the TruTag app on their smartphone, which will be used to measure daily adherence for 90 days.

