Potential participants will be approached and pre-screened. Those who meet pre-screening criteria will attend a Screening Visit (Visit 1), where the informed consent process will be conducted and study eligibility will be confirmed. Eligible participants will attend four additional visits over the course of the study – the Enrollment Visit (Visit 2), Month 1 Visit (Visit 3), Month 2 Visit (Visit 4), and Month 3 Visit (Visit 5). Participants will take one ART pill per day, for 90 days total, while using the TruTag system and app. The app will facilitate reminders and serve as a two-way text communication platform between participants and the study team. Simple reminders will be sent following detected nonadherence with the aim of improving ART adherence. Timeline followback discussions will be conducted at the Month 1, Month 2, and Month 3 Visits to understand the context of any detected nonadherence. Dried blood spots (DBS) will be conducted at the Screening Visit (Visit 1) and the Month 3 Visit (Visit 5). Qualitative exit interviews will be conducted at the Month 3 Visit (Visit 5).

4. Participant Selection.

Recruitment. Individuals will be recruited through social media, flyering, and community outreach events in partnership with HIV advocacy groups and organizations serving LGBT populations in the greater Boston area. We will coordinate recruitment efforts with the recruitment team at The Fenway Institute (TFI), a dedicated group that assist research teams with identifying and matching potential participants with ongoing research studies at Fenway Health. The data team at TFI additionally compiles and generates periodic reports using specific inclusion criteria to generate lists of potentially eligible patients interested in participating in research. We will utilize a HIPAA waiver to obtain these reports from the Fenway Health electronic health record, and, following the identification of potentially eligible individuals, will contact primary care providers (PCPs) via email to obtain clearance to contact their patients, as needed per Fenway Health policy. We will contact interested individuals to explain the study in more detail and conduct a brief pre-screening to confirm eligibility.

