Pre-screening. All interested individuals will undergo a pre-screening process, conducted via phone or in-person by a study RA, student intern, or other trained study team member, to evaluate preliminary eligibility. A Pre-Screen ID number will be assigned to each individual during this process. Data collected during pre-screening will be recorded in a password-protected spreadsheet or within REDCap hosted at TFI.

Informed Consent. Individuals who meet pre-screening criteria will be scheduled for a Screening Visit (Visit 1), where we will conduct the informed consent discussion and obtain written consent. A trained study RA will review the consent form with the individual in detail, discuss the overall goals of the study, and review all procedures. Individuals will be asked to voice their understanding of the information and will have adequate time to ask questions. If they agree to participate, they will be asked to sign the informed consent form and will be provided with a copy for their records. Informed consent discussions will take place in private consult rooms at TFI.

Inclusion Criteria		Exclusion Criteria	
1)	Age 18 or older	1)	Not English-speaking
2)	Living with HIV	2)	Unwilling to interact with the TruTag app
3)	Currently prescribed and taking Biktarvy as ART for at least 3 months		
4)	Undetectable viral load in prior 6 months		
5)	Owns iPhone model 11 or higher (non-SE only)		

5. Participant Enrollment.

Once the informed consent form and Medical Release Form have been signed, study staff will confirm eligibility. Individuals will be asked to provide their most recent viral load results to confirm undetectable viral load during the prior 6 months. If they do not have recent viral load results, study staff will obtain an HIV viral load during this visit, or, if preferred, individuals can obtain a viral load from their HIV care provider. Individuals who meet all criteria will be scheduled for an Enrollment Visit (Visit 2).

6. Study Procedures.

Study Visits. There are a total of five visits during the study period: the Screening Visit (Visit 1), Enrollment Visit (Visit 2), Month 1 Visit (Visit 3), Month 2 Visit (Visit 4), and Month 3 Visit (Visit 5).

[figure not shown]

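### Section 9 compares TruTag with the other adherence measures only by correlation, which cannot by itself show how well TruTag records doses; a paired agreement measure should be added

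*Combined protocol and SAP*

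**What the plan says.** Section 6 (Study Outcomes) makes feasibility and acceptability the primary outcomes. The correlation of TruTag-recorded adherence with other adherence measures is the secondary outcome. Section 9 lists three measures (TruTag record, pill count at each monthly visit, DBS concentration) and then states: "Correlation coefficients will be calculated between each of these adherence metrics". The only other comparative statistic is a point biserial correlation, meant to show whether the relationship weakens over time. Section 9 gives no type of coefficient, confidence interval, unit of analysis or measure of agreement.

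The sample is small and selected. Section 3 states "We will enroll N=15 individuals living with HIV who are taking" the study drug. The inclusion criteria in Section 4 require "Undetectable viral load in prior 6 months" and "Currently prescribed and taking Biktarvy as ART for at least 3 months". Section 3 adds: "Simple reminders will be sent following detected nonadherence with the aim of improving ART adherence".

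On the data, Section 6 (TruTag System) says "A corresponding app records each scan as an adherence event", and Section 6 (Data Collection) says "Study staff will collect participant monthly adherence via the TruTag application". DBS is taken at Screening and Month 3, so one sample per person falls within TruTag use.

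**The concern.** The natural question for the secondary outcome is what share of the doses taken TruTag captures. A correlation answers a different question: whether people who rank high on one measure rank high on the other. That creates two problems.

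- **Dependence on spread.** The same recording system gives a low r when everyone's adherence is similar and a high r when it varies. Entry on suppressed virus, followed by reminders, makes a narrow spread plausible.
- **Blindness to systematic loss.** If every participant's scans fall short by the same number or the same proportion, r does not change. Random loss does lower r, but the same fall can come from a narrow spread.

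A low r could therefore be read against a system that records well, and a high r in favour of one that misses many doses. With at most 15 people and no interval planned, the reader would also not see how uncertain the value is.

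**Working it through.** **Inputs from the documents.** n=15; 90 days at one pill per day (Section 3); three monthly TruTag and pill-count values per person; one on-study DBS value per person. The plan gives no target correlation, precision or justification for N=15, so it has no figure to reproduce.

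**Assumed inputs.** The documents give no adherence distribution and no scan accuracy. Three adherence distributions were tried: mean 97%/SD 3 points, 95%/SD 4.8 and 90%/SD 9. Two recorders were tried: one captures on average 95% of taken doses (person-level fidelity Beta(38,2)), the other 60% (SD 3 points between people). Pill count is taken as exact.

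**Step 1: precision at n=15.** The Fisher interval is tanh(atanh(r) ± 1.96/√(n-3)), and 1.96/√12 = 0.566.
- r=0.5: atanh = 0.549, limits -0.017 and 1.115, giving **-0.02 to 0.81**.
- r=0.7: atanh = 0.867, limits 0.301 and 1.433, giving **0.29 to 0.89**.

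The formula assumes bivariate normality, so near a ceiling it is approximate.

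**Step 2: spread, by hand.** If s is the between-person SD of true adherence and e the SD of independent recording error, r = s/√(s²+e²). With e = 5 points, s = 3 gives 3/√34 = 0.51 and s = 10 gives 10/√125 = 0.89. The recorder is the same in both.

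**Step 3: spread, by simulation.** For each person, draw adherence p from a beta distribution, doses taken T ~ Binomial(90, p), and scans S ~ Binomial(T, f). Then correlate S with T over 15 people.
- 95% recorder, 97%/SD 3: median r **0.65** (95% of trials about 0.1 to 0.91).
- 95% recorder, 95%/SD 4.8: median r **0.79** (about 0.36 to 0.95).
- 95% recorder, 90%/SD 9: median r **0.93** (about 0.7 to 0.98).
- 60% recorder, 90%/SD 9: median r **0.72**, above the 0.65 of the 95% recorder in the narrow sample.

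A different coefficient does not cure this. For the 95% recorder, between the first and third distributions, Spearman's coefficient moves from 0.58 to 0.87 and a within-participant correlation from 0.60 to 0.81.

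**Step 4: recording accuracy also moves r.** With adherence held at 97%/SD 2, median r is 0.27 for a 60% recorder (SD 3), 0.40 for a 90% recorder (SD 5) and 0.59 for a 95% recorder (SD 3). So r mixes the two influences.

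**Step 5: paired difference.** The expected mean of TruTag minus pill count, in percentage points, is -(mean adherence) × (1 - fidelity).
- 95% recorder: -97×0.05 = -4.9; -95×0.05 = -4.8; -90×0.05 = -4.5.
- 60% recorder: -97×0.40 = -38.8; -95×0.40 = -38.0; -90×0.40 = -36.0.

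The difference separates the recorders at every spread tried.

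**Step 6: unit of analysis.** TruTag and pill count give up to 15×3 = 45 person-months. Taken as 45 independent rows, 1.96/√42 = 0.302 and the interval for r=0.5 shrinks to 0.24 to 0.69. With a true correlation of 0.5, simulated coverage of that nominal 95% interval is about 90% at an assumed within-person correlation of 0.5 and 83% at 0.7.

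**The case against.** This is a 15-person open-label pilot whose primary outcomes are feasibility and acceptability. No test, validity threshold or go/no-go decision depends on r, and the monthly timeline followback gives context for missed scans. That stands, and it limits the weight of the point. It does not remove it: correlation is the declared secondary outcome and the only planned statistic comparing the measures, and no agreement statistic is planned from the followback.

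Three stronger readings are tempting, and the documents do not support them.

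- **That r would mainly reflect spread and not recording.** This depends on the spreads assumed. Step 4 shows accuracy moving r as well.
- **That adherence will sit near 100%.** One undetectable result in the prior 6 months and 3 months on treatment make a narrow range likely, but do not fix adherence over the next 90 days. Section 9 itself anticipates that some participants may stop using the system, which would widen the TruTag values.
- **That the plan pools 45 person-months as independent.** It does not say so; month-by-month correlations on 15 people fit the text equally well. Step 6 describes a risk left open.

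Pill count is also not a perfect standard, so a paired difference shows agreement with pill count, not with the true number of doses swallowed.

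**Conclusion.** The point holds as a limit on what the secondary outcome can show. Correlation alone, in at most 15 selected participants, cannot establish how well TruTag records doses. The interval at n=15 (-0.02 to 0.81 for r=0.5) needs only n and r, plus the usual approximation. The sizes of the spread effect (0.65 to 0.93 for one recorder) and of the reversal (0.72 for a much poorer one) rest on assumed adherence, assumed scan fidelity and an exact pill count. The direction does not, because it follows from what a correlation measures.

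A reader might infer that r=0.5 would be compatible with anything from no agreement to very strong agreement. That is not the conclusion: the interval concerns association, and neither limit says anything about agreement. Nor does the point show that N=15 is wrong for a feasibility study.

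**What to change.** Amend Section 9 as follows.

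1. **Agreement, TruTag versus pill count.** Report the paired difference (TruTag minus pill count) with limits of agreement, and the share of pill-count doses that were scanned, with a 95% CI clustered by participant. State that this share is an aggregate ratio, because a pill count does not date individual doses.
2. **Planned correlations.** Keep them and name the coefficient. Use the participant as the unit, with a 95% CI from resampling participants and the SD and range of each measure printed beside it. Pair only the Month 3 DBS with on-study TruTag adherence, in line with the Month 3 Visit text in Section 6. DBS is a concentration, so the paired difference in item 1 does not apply to it.
3. **Monthly values.** If monthly TruTag and pill-count values are used together, analyse them as repeated measures within participant, not as 45 independent rows.

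The cost is a paragraph of SAP text and a little more analysis on data already to be collected. The downside is that the reported intervals will be visibly wide.
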